7.6.3 Determination of Dose-limiting toxicity

The patient population used for determination of MTD will consist of patients who have met the minimum safety evaluation requirements of the study, and/or who have experienced a DLT. The data of at least 3 patients will be required for DLT assessment.

- DLT assessment period will be 28-days (inclusive) (will begin on C1D1 and end on C2D1), unless extended by the medical monitor.
- Patients must have been treated with at least 2 doses of Romidepsin and minimum 14 days with Tenalisib in the first cycle to be considered eligible for safety assessment unless identified to have a DLT.
- *Patients experiencing DLT after initiating combination will be considered evaluable regardless of the number of doses received (Please note Romidepsin alone will be administered on Day 1, therefore patient will not be considered for MTD assessment if patient develops DLT on these days).*

If a patient withdraws from the study during Cycle 1 due to any reason other than DLT (e.g. disease progression or consent withdrawal) and does not meet the minimum requirements for inclusion in the MTD-determining population described above will be replaced.

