3.2.1 Phase I: Dose Escalation

3.2.1.1 Dose Escalation Cohorts

Sequential dose escalation will begin with Cohort 1. A minimum of three patients will be enrolled at each dose level. Dose levels will be increased in successive increments according to the dose escalation cohorts mentioned in Table 1. Escalation to the next cohort will occur if no patient within a three-patient cohort or one in six patients experiences a dose limiting toxicity (DLT). De-escalation to different lower doses in case of DLT criteria met will be done as per the discretion of the Safety Review Committee (SRC). The highest doses of the combination (Tenalisib at 800 mg BID plus Romidepsin IV 14 mg/m²) will be considered as optimal in case there is no DLT at this dose level.

Table 1: Dose Escalation Scheme

Cohort	N	Tenalisib ¹	Romidepsin ²
Cohort 1	3-6	Tab. 400 mg PO twice a day	IV 12 mg/m ² on Day 1, 8 and 15
Cohort 2	3-6	Tab. 600 mg PO twice a day	IV 12 mg/m ² on Day 1, 8 and 15
Cohort 3	3-6	Tab. 800 mg PO twice a day	IV 14 mg/m ² on Day 1, 8 and 15

Note: Alternate dose levels/dosing schedules may be considered by the SRC if deemed essential based on emerging safety and PK data.

¹*In case the dose (e.g. 800 mg BID) is leading to DLT of the combination, the dose of Tenalisib will be reduced to lower dose (e.g. 600 mg BID) and will be evaluated for safety in a separate cohort.*

²*In case the dose (e.g. 14 mg/m²) is leading to DLT of the combination, the dose of Romidepsin will be reduced to lower dose (e.g. 12 mg/m²) and if required further to 10 mg/m² and will be evaluated for safety in a separate cohort.*

Notes:

- For dose escalation decision, safety data of the first 28-days follow up and PK data of C1D1 and C1D8 is essential.
- The dose escalation may occur if no patient within a three-patient cohort experiences a DLT as defined in Section 7.6 If one of three patients within a 3-patient cohort experiences

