3.6 Study Stopping Rules

3.6.1 Stopping Rule for Dose Escalation

The SRC will be in charge of reviewing safety data following the final treatment dose (Day 28 of Cycle 1) of the last patient in each cohort and will decide whether or not it is possible to proceed to the next cohort according to the dose escalation procedure described in Section 3.2.1.1. In order to ensure safety and limit toxicity for enrolled patients, dose modifications will be performed according to the procedure described in Section 7.7.

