6.12 End of Trial Treatment (EOT) Visit

Post C8D1, patients experiencing clinical benefit with no evident disease progression will be given the opportunity to enroll in an open-label compassionate use study protocol and will be followed up. Excluding patients who participate in the compassionate use study protocol, all other patients will undergo the end-of-treatment (EOT) assessments within 7 days after the last dose of study drug or discontinuation from the study. Radiological assessment and bone marrow biopsy will not be performed if done earlier within 28 days.

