6.13 End of Study (EOS) Visit

All patients must be followed up telephonically for adverse events for 30 calendar days after the last dose of study drug. In case of drug related SAE/AE or treatment discontinuation due to adverse event, the subjects will be followed till the resolution/stabilization of the AE or 30 days after the last study dose whichever is the earlier

Table 5: Schedule of Events for Dose Escalation

	Screening	Cycle 1					Cycle 2				Cycle 3			Cycle 4-7			EOT ²⁴ /C8D1	EOS ²⁵
Day	D-28 to 0	D1	D3	D8	D15	D22	D1	D8	D15	D22	D1	D8	D15	D1	D8	D15	D1	-
Window period	-28	0	-	±1	±1	±1	±1	±1	±1	±1	±1	±1	±1	±1	±1	±1	+7	+30
Study Days	D-28 to 0	1	3	8	15	22	29	36	43	50	57	64	71	-	-	-	197	227
Informed Consent ¹	X	-	-	-	-	-	-	-	-	-	-	-	-	-	-	-	-	-
Demographics ²	X	-	-	-	-	-	-	-	-	-	-	-	-	-	-	-	-	-
Medical history ³	X	-	-	-	-	-	-	-	-	-	-	-	-	-	-	-	-	-
Vitals ⁴	X	X	-	X	X	X	X	X	X	X	X	X	X	X	X	X	-	-
Height and weight ⁵	X	X	-	X	X	X	X	X	X	X	X	X	X	X	X	X	-	-
Complete Physical exam ⁶	X	-	-	-	-	-	-	-	-	-	-	-	-	-	-	-	-	X
Abbreviated Physical exam ⁶	-	X	-	X	X	-	X	X	X	-	X	X	X	X	X	X	-	-
ECOG Performance Status	X	X	-	-	-	-	-	-	-	-	X	-	-	-	-	-	X	-
Tumor staging	X	-	-	-	-	-	-	-	-	-	-	-	-	-	-	-	-	-
Laboratory assessment																		
Complete blood count ⁷	X	X	-	X	X	X	X	X	X	X	X	X	X	X	X	X	-	-
Chemistry panel I ⁸	X	X	-	X	X	X	X	X	X	X	X	X	X	X	X	X	-	-
Chemistry panel II ⁹	X	X	-	-	-	-	-	-	-	-	X	-	-	X	-	-	X	-
Serology ¹⁰	X	-	-	-	-	-	-	-	-	-	-	-	-	-	-	-	-	-
PT and INR ¹¹	X	X	-	X	X	X	X	X	X	X	X	X	X	X	X	X	-	-
Urinalysis (routine)	X	X	-		X	-	X	-	X	-	X	-	X	-	X	-	X	-
Pregnancy test ¹²	X	X	-	-	-	-	X	-	-	-	X	-	-	X	-	-	X	-
12-lead ECGs ¹³	X	X	-	X	X	-	X	-	-	-	X	-	-	X	-	-	X	-
Pharmacokinetic samples ¹⁴	-	X	-	X	-	-	X	-	-	-	X	-	-	X	-	-	-	-
Bone marrow biopsy ¹⁵	X	-	-	-	-	-	-	-	-	-	-	-	-	-	-	-	-	-

Skin biopsy ¹⁶	X	-	-	-	-	-	-	-	-	-	-	-	-	-	-	-	-
Disease assessment																	
Radiological scan/imaging ¹⁷	X	-	-	-	-	-	-	-	-	X	-	-	-	-	-	X	-
mSWAT ¹⁸	X	-	-	-	-	-	-	-	-	X	-	-	-	-	-	X	-
Skin photographs ¹⁹	X	-	-	-	-	-	-	-	-	-	-	-	-	-	-	-	-
Correlative markers ²⁰	X	-	-	-	-	-	-	-	-	X	-	-	-	-	-	-	-
Treatment administration																	
Tenalisib ²¹	-	-	X	X	X	X	X	X	X	X	X	X	X	X	X	-	-
Romidepsin infusion ²²	-	X	-	X	X	-	X	X	X	-	X	X	X	X	X	-	-
Drug compliance	-	X	-	X	X	X	X	X	X	X	X	X	X	X	X	X	-
Safety evaluation																	
AE evaluation ²³	X	X	-	X	X	X	X	X	X	X	X	X	X	X	X	X	X
SAE evaluation	X	X	-	X	X	X	X	X	X	X	X	X	X	X	X	X	X
Concomitant medication	X	X	-	X	X	X	X	X	X	X	X	X	X	X	X	X	X

Foot notes:

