7.6.4 Maximum Tolerated Dose (MTD)

The MTD is the highest dose of the combination at which 0 of 3 patients or 1 of 6 patients experience a DLT during 1 cycle (28 days) of therapy. If 2 or more patients in a dosing group experience a DLT, the MTD has been exceeded.

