### Dose escalation scheme:

Cohort	N	Tenalisib 	Romidepsin 
Cohort 1	3-6	Tab. 400 mg PO twice a day	IV 12 mg/m  on Day 1, 8 and 15
Cohort 2	3-6	Tab. 600 mg PO twice a day	IV 12 mg/m  on Day 1, 8 and 15
Cohort 3	3-6	Tab. 800 mg PO twice a day	IV 14 mg/m  on Day 1, 8 and 15

Note: Alternate dose levels/dosing schedules may be considered by the SRC if deemed essential based on emerging safety and PK data.

In case the dose (e.g. 800 mg BID) is leading to DLT of the combination, the dose of Tenalisib will be reduced to lower dose (e.g. 600 mg BID) and will be evaluated for safety in a separate cohort.

In case the dose (e.g. 14 mg/m^2) is leading to DLT of the combination, the dose of Romidepsin will be reduced to lower dose (e.g. 12 mg/m^2) and if required further to 10 mg/m^2 and will be evaluated for safety in a separate cohort.

**DLT assessment:** The data of at least 3 patients will be required for DLT assessment. DLT assessment period will be 28-days (inclusive) (will begin on C1D1 and end on C2D1), unless extended by the medical monitor. In the first cycle, patients must have been treated with at least 2 doses of Romidepsin and minimum 14 days with Tenalisib to be considered eligible for safety analysis unless identified to have a DLT. Patients who experience a DLT will be considered evaluable regardless of the number of doses received.

Individual patients will be considered for **Intra-subject dose escalation** at the discretion of investigator after discussion with medical monitor.

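### The dose-limiting toxicity (DLT) evaluability and replacement rules set only a dose minimum, reachable on Day 16, and do not require observation to the end of the 28-day window

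*Protocol*

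**What the plan says.** Protocol 7.6.3 sets a DLT assessment period of 28 days, from C1D1 to C2D1, which the medical monitor may extend. For a patient without a DLT it then states: "Patients must have been treated with at least 2 doses of Romidepsin and minimum 14 days with Tenalisib in the first cycle". The replacement sentence covers a patient who withdraws "during Cycle 1 due to any reason other than DLT (e.g. disease progression or consent withdrawal) and does not meet the minimum requirements".

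SAP 5.1 (dose escalation scheme, DLT assessment) repeats the dose condition: "patients must have been treated with at least 2 doses of Romidepsin and minimum 14 days with Tenalisib to be considered eligible". The synopsis has the same wording. Neither carries the replacement rule.

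The 28-day window appears in three other places:
- MTD definition (7.6.4): none of 3 or "1 of 6 patients experience a DLT during 1 cycle (28 days) of therapy".
- Escalation notes (3.2.1.1): "For dose escalation decision, safety data of the first 28-days follow up and PK data of C1D1 and C1D8 is essential".
- Safety Review Committee (SRC) review (3.6.1, repeated in SAP 5.3): "reviewing safety data following the final treatment dose (Day 28 of Cycle 1) of the last patient in each cohort".

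Two follow-up provisions apply to a patient who stops early. Section 6.12 says "all other patients will undergo the end-of-treatment (EOT) assessments within 7 days after the last dose of study drug". Section 6.13 says "All patients must be followed up telephonically for adverse events for 30 calendar days after the last dose of study drug", and 7.1.3 requires the same 30 days.

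**The concern.** The rule that decides which DLT-free patients count is written in doses. The quantity being estimated is the occurrence of a DLT over 28 days. A patient who has met the dose minimum and leaves on about Day 17 is not caught by the replacement sentence, and nothing else in 7.6.3 removes that patient from the count. The patient then stands as DLT-free with up to 12 of the 28 days unobserved, including almost all the time after the Day 15 Romidepsin dose.

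A missed DLT can only lower the observed count, so the error runs in one direction, toward escalation. The MTD is a primary objective, rests on 3 to 6 patients per cohort, and fixes the dose for the 24 expansion patients. With cohorts this small, one misclassified patient can decide whether the dose goes up.

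**Working it through.** **Plan's own figures.** Day 1 to Day 28 inclusive is 28 days, and C2D1 is study day 29 (Table 5), so the stated window reproduces. The maximum of 18 patients is 3 cohorts × 6.

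**Earliest evaluable day.** Romidepsin is given on Days 1, 8 and 15 (5.2), so the second dose falls on Day 8. Tenalisib starts on Day 3 in Cycle 1 of escalation (5.1), so 14 days end on Day 3 + 14 − 1 = Day 16. The minimum can be met on max(8, 16) = Day 16. Missed Tenalisib days push this later.

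**What follow-up covers.** With a last dose on Day 16, the end-of-treatment (EOT) visit falls by Day 16 + 7 = Day 23, and adverse-event follow-up runs to Day 16 + 30 = Day 46, past C2D1. That follow-up may be by telephone. Several DLT criteria in 7.6.1 and 7.6.2 depend on laboratory values (Grade 4 neutropenia, Grade 4 thrombocytopenia, Grade 3 or higher ALT/AST elevation). A call cannot detect these unless blood is drawn. Table 5 schedules blood counts and Chemistry Panel I on Day 22 and at C2D1, both after Day 16.

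**Effect on the 3+3 rule.** The documents give no DLT rate for the combination, no onset pattern and no early-leaving rate. The following are assumptions:
- true 28-day DLT rate p = 25%, 33% or 40%;
- DLT onset uniform over Days 3 to 28 (26 days);
- one leaver, seen to Day 23 (f = 21/26 = 0.808) or only to Day 16 (f = 14/26 = 0.538);
- the leaver's observed DLT probability is q = p × f.

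P(escalate) = P(0 of first 3) + P(1 of first 3) × P(0 of next 3).

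Full observation, p = 0.33: 0.67³ = 0.3008; 3 × 0.33 × 0.67² = 0.4444; 0.3008 + 0.4444 × 0.3008 = 0.4344.

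One leaver among the first three, p = 0.33:
- Seen to Day 23: q = 0.2665. P(0) = 0.7335 × 0.4489 = 0.3293. P(1) = 0.2665 × 0.4489 + 0.7335 × 2 × 0.33 × 0.67 = 0.4440. Escalate: 0.3293 + 0.4440 × 0.3008 = 0.4628.
- Seen to Day 16: q = 0.1777. P(0) = 0.8223 × 0.4489 = 0.3691. P(1) = 0.1777 × 0.4489 + 0.8223 × 0.4422 = 0.4434. Escalate: 0.3691 + 0.4434 × 0.3008 = 0.502.

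| True DLT rate | Full observation | Leaver in first three (Day 23; Day 16) | Leaver in second three (Day 23; Day 16) |
|---|---|---|---|
| 25% | 60.0% | 62.3%; 65.6% | 61.1%; 62.7% |
| 33% | 43.4% | 46.3%; 50.2% | 44.7%; 46.5% |
| 40% | 30.9% | 33.9%; 38.1% | 32.1%; 33.8% |

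**Onset sensitivity** (33%, leaver in first three, seen to Day 16). Uniform onset puts 12/26 = 46% of DLTs after Day 16. If 25% start after Day 16, the chance of escalating is 47.1%; if 60% do, 52.3%.

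**Averaged over leaving.** If each of six patients leaves this way with chance L, the observed DLT probability per patient is p × [1 − L × (1 − f)]. At p = 0.33:
- L = 5%: rise of 0.6 points (f = 0.808) to 1.5 points (f = 0.538).
- L = 10%: rise of 1.2 to 3.0 points.
- If follow-up captures 90% to 95% of a leaver's DLTs (f = 0.90 to 0.95, also assumed): about 0.2 to 0.3 points at L = 5%, and 0.3 to 0.6 at L = 10%.

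**The case against.** The strongest reply is that the dose minimum is worded as a floor. It says what a patient must have received, not that receiving it is enough. The 28-day period is listed just above it, and the requirements that the replacement sentence refers back to could be read to include that period. Section 3.2.1.1 goes further than a timing rule: it names 28 days of safety data as needed for the escalation decision. A patient who stops for progression still has the EOT visit and 30 days of adverse-event follow-up.

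Much of this stands. A reader might infer that the plan declares doses alone sufficient, or that it intends to escalate on 16 days of data. The documents do not support either reading: 3.2.1.1 and 7.6.4 show the opposite intent, and 3.6.1 places the SRC review after Day 28 of the last patient.

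It does not close the gap. No sentence makes observation to C2D1 a condition of evaluability, and none orders replacement of a dose-qualified leaver. Section 3.2.1.1 does not say what happens to such a patient, so it conflicts with the replacement rule rather than repairing it. Section 3.6.1 sets when the SRC reviews a cohort, not who is counted. Follow-up narrows the gap but cannot reach patients who withdraw consent or are lost, and a telephone call does not replace a missed blood test.

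**Conclusion.** The inconsistency is real and worth correcting, but narrow. The evaluability and replacement wording does not require observation to C2D1, which does not match the 28-day MTD definition or the statement that 28-day safety data are essential. It matters mainly for withdrawn consent, loss to follow-up or missed laboratory tests between about Day 17 and C2D1. A late DLT that is found would still count.

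The average effect is probably small: at most about 0.6 to 3.0 points at a 33% DLT rate and 5% to 10% leaving, and less if the 30-day follow-up finds most late DLTs. The conditional effect of one leaver among the first three is larger, from 43.4% to about 46% if seen to Day 23. A reader might take the 50% figure as the expected effect. It is not: it assumes that a leaver has already occurred and that neither the EOT visit nor the 30-day contact yields anything, and so is an upper bound under uniform onset. The direction does not depend on the assumed rates. The sizes do, and none of those rates is in the documents.

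**What to change.** In 7.6.3, SAP 5.1 and the synopsis, state that a patient without a DLT is evaluable only if the dose minimum is met and safety observation, including the scheduled laboratory tests, is complete to C2D1. State in the same place that any DLT-free patient who does not complete this is replaced.

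Events still open at C2D1 are a separate matter, since they concern patients who finished the window. An event starting on Day 16 reaches a 14-day test on Day 30, one day after C2D1. If the sponsor adds a rule for these, it should cover every criterion with a 14-day element in 7.6.1 and 7.6.2: Grade 4 neutropenia, febrile neutropenia, Grade 4 thrombocytopenia, Grade 3 or higher thrombocytopenia with bleeding, Grade 3 or higher ALT/AST elevation, and treatment delay of 14 days or more. Otherwise leave it out; a partial list would treat similar criteria differently.

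The cost is one or two sentences in each document, an occasional replacement patient and slightly slower escalation. The optional rule for open events could add up to about two weeks' wait. If escalation is already complete, the report can still state which DLT-free patients were observed to C2D1.

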7.6.4 Maximum Tolerated Dose (MTD)

The MTD is the highest dose of the combination at which 0 of 3 patients or 1 of 6 patients experience a DLT during 1 cycle (28 days) of therapy. If 2 or more patients in a dosing group experience a DLT, the MTD has been exceeded.

7.7 Dose Modifications

All dose modifications are graded by the CTCAE v5.0.

Note: If cytopenia events are deemed related to the underlying disease rather than either Tenalisib or Romidepsin, dose reduction will be done as per the investigator's discretion.

Patients who experience either a DLT or an adverse event meeting DLT criteria (that occurs after the DLT assessment window) will be allowed to delay dosing in order to recover from the toxicity. Patients may resume Tenalisib, provided that the toxicity has resolved to Grade ≤ 2 or baseline. If study drug is delayed >2 weeks due to drug toxicity, treatment initiation should be discussed and agreed with the Medical Monitor.

Dose reductions will be permanent. A dose re-escalation are not permitted for patients who previously had a dose reduction. Holidays from study drug are discouraged. Any patient in whom similar toxicity recurs at the reduced dose should be discontinued from further Tenalisib treatment. Note: In exceptional case, a patient may be allowed following a careful assessment of benefit and risk by the investigator and with approval from the Medical Monitor.

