7.7.1 Criteria for Re-Starting Tenalisib after Drug toxicity

Treatment continuation in the study is at the discretion of the treating Investigator. In the absence of unacceptable toxicities or disease progression, patients may continue treatment with Tenalisib as long as:

- Absolute neutrophil count has returned to baseline, or $>750/\mu\text{L}$. Platelet count is $>50,000/\mu\text{L}$.
- Recovered from grade 3-4 non-hematologic toxicity to grade 2 or baseline (excluding alopecia). Treatment may be delayed for up to 2 weeks to recover from toxicity.
- No clinical or radiographic evidence of disease progression.
- If treatment is delayed > 2 weeks due to toxicity, because of an adverse event, treatment initiation should be discussed and agreed with the Medical Monitor.

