7.7.2.1 Tenalisib Dose Modifications for Hematologic Toxicity

The dose modification guidelines are intended to be applied when the investigator determines the events related to Tenalisib.

Table 7: Dose Modifications for Hematologic Toxicity

Worst CTCAE Grade Toxicity	Action to be Taken
HEMATOLOGIC	
Neutropenia (ANC)	
Grade 3 $1.0 \times 10^9 / L < ANC \geq 0.5 \times 10^9 / L$	Maintain dose level. Monitor ANC at least weekly. Restart Tenalisib when the event resolved to \leq Grade 2 or baseline.
Grade 4 $0.5 \times 10^9 / L < ANC$	First incidence: Hold* dose until resolved to \leq Grade 2 or baseline, Restart Tenalisib at one dose lower . Subsequent occurrence: Hold dose until resolved to \leq Grade 2 or baseline, consider growth factor support. Discontinue if further dose modification required.
Grade 3 Febrile neutropenia ANC $< 1000 / \text{mm}^3$ with a single temperature of $> 38.3^{\circ}\text{C}$ (101°F) or a sustained temperature of $\geq 38^{\circ}\text{C}$ (100.4°F) for more than one hour.	Hold* dose until resolved to \leq Grade 2 or baseline, consider growth factor support, then restart Tenalisib at one dose lower .
Thrombocytopenia	
Grade 3 ($50.0 \times 10^9 / L < PLT \geq 25.0 \times 10^9 / L$)	Maintain dose level. Monitor ANC at least weekly. Restart Tenalisib when the event resolved to \leq Grade 2 or baseline.
Grade 4 $25.0 \times 10^9 / L < PLT$ Or thrombocytopenia that requires platelet transfusion	1st occurrence: Hold** dose until to \leq Grade 2 or baseline, Restart Tenalisib at one dose lower. Subsequent Occurrences: Hold dose until to \leq Grade 2 or baseline, consider platelet transfusion as necessary. Discontinue if further dose modification required.

*If study drug is delayed > 2 weeks because of an adverse event, treatment strategy should be discussed with medical monitor.

** Patient receiving concomitant medication (e.g. anticoagulants, anti-platelets, aspirin, or low molecular weight heparin) must be discussed with the medical monitor for continued management.

Table 8: Dose Modifications for Non-Hematologic Toxicities

NON-HEMATOLOGIC	Action to be Taken
Renal*	If serum creatinine is Grade 3 ($> 3 \times$ baseline or $> 3 \times$ ULN), hold dose until \leq grade 2. Monitor serum creatinine at least twice a week until resolution to \leq grade 2, and then at least one week until it resolves to \leq grade 1.

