Cardiac	
If a QTcF >500 msec has been demonstrated, hold dose.
 
The patient will be monitored hourly with ECGs until the QTcF <500 msec and the QTcF has returned to "<30 msec from baseline". Immediate attention to potassium and magnesium and other clinical factors such as oxygenation and ischemia should be addressed.
 
All cardiac events should be treated as per the local standard of care and referral to a specialist if clinically indicated. Any final decisions concerning dose modifications or permanently discontinuing the patient from study drug due to QTcF prolongation will occur after discussion with medical monitor.

OTHER NON-HEMATOLOGIC	Action to be Taken
Grade 3/4 CTCAE	
First occurrence: Hold* dose until toxicity Grade \leq 2; restart Tenalisib at one dose lower.
 
Subsequent Occurrences: Hold dose until to \leq Grade 2 or baseline. Discontinue if further dose modification required.

* If study drug is delayed >2 weeks because of an adverse event, treatment strategy should be discussed with medical monitor.

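### When toxicity recurs at the reduced dose, Section 7.7 stops Tenalisib unless the Medical Monitor approves an exception; three cells of Tables 7 and 8 hold it and stop only conditionally

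*Protocol*

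**What the plan says.** Section 7.7 of the Protocol makes dose reductions permanent and then deals with recurrence: "Any patient in whom similar toxicity recurs at the reduced dose should be discontinued from further Tenalisib treatment". The single exception is for an exceptional case, where "a patient may be allowed following a careful assessment of benefit and risk by the investigator and with approval from the Medical Monitor".

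Tables 7 and 8 sit under Section 7.7.2. Table 7 is introduced with its scope: "The dose modification guidelines are intended to be applied when the investigator determines the events related to Tenalisib". For a first Grade 4 neutropenia or Grade 4 thrombocytopenia it orders a hold and a restart one dose lower. For a later occurrence it again orders a hold until Grade 2 or less or baseline, and then:

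- Grade 4 neutropenia: "consider growth factor support. Discontinue if further dose modification required".
- Grade 4 thrombocytopenia: "consider platelet transfusion as necessary. Discontinue if further dose modification required".

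The last row of Table 8, for other Grade 3/4 non-hematologic toxicity, follows the same pattern. On a later occurrence the dose is held until the event is at or below "Grade 2 or baseline. Discontinue if further dose modification required".

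Section 7.7.1 adds: "Treatment continuation in the study is at the discretion of the treating Investigator". It continues: "In the absence of unacceptable toxicities or disease progression, patients may continue treatment with Tenalisib as long as" certain count, recovery and progression conditions are met. It does not mention recurrence and does not define which toxicities are unacceptable.

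**The concern.** After the first event these three rows restart Tenalisib one dose lower, so a second similar event normally happens at the reduced dose. That is the situation the recurrence rule in Section 7.7 describes. Section 7.7 makes stopping the default and puts the Medical Monitor in front of any exception. The cells make holding the default and name no approval.

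The synopsis plans about 15 centers. A patient with a second Grade 4 cytopenia attributed to Tenalisib could be stopped at one site and, at another, re-exposed without the approval that Section 7.7 requires. What is at stake is patient protection and uniform conduct in a trial whose primary objective is safety and tolerability. There is also a reporting consequence. SAP Sections 10.1 and 10.6.2 count interruptions separately from permanent discontinuations, so the same clinical course can be counted differently according to the rule the site applied.

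**Working it through.** No figure in the plan needs reproducing. The check sets each row that restarts Tenalisib one dose lower against the recurrence rule in Section 7.7.

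| Row | Text on recurrence | Compared with 7.7 |
|---|---|---|
| Table 7, Grade 4 neutropenia | Hold; stop if further modification is needed | Conflicts |
| Table 7, Grade 3 febrile neutropenia | None | 7.7 governs alone |
| Table 7, Grade 4 thrombocytopenia | Hold; stop if further modification is needed | Conflicts |
| Table 8, Grade 3 or higher transaminitis | Stop permanently after weighing risk and benefit | Same default; approval not named |
| Table 8, Grade 3 or higher bilirubin | None | 7.7 governs alone |
| Table 8, severe diarrhoea | None | 7.7 governs alone |
| Table 8, other Grade 3/4 | Hold; stop if further modification is needed | Conflicts only if the same or a similar toxicity recurs |

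Count: 3 rows in Table 7 + 4 in Table 8 = 7, made up of 2 in conflict, 1 in partial conflict, 1 sharing the default without the approval step, and 3 silent. The last row is partial because it pools unlike toxicities, and Section 7.7 says nothing about a different one.

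**Test case.** A patient has Grade 4 neutropenia attributed to Tenalisib, recovers, restarts one dose lower, and has Grade 4 neutropenia again.

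1. Recovery within 2 weeks, Tenalisib alone suspected. Section 7.7 says stop unless an exception is approved. Table 7 says hold, and stop only if a further modification is needed. Section 7.7.1 leaves continuation to the investigator. The instructions differ and no text ranks them.
2. Recovery takes more than 2 weeks. Sections 7.7 and 7.7.1 require the Medical Monitor's agreement before treatment resumes, whichever rule the site follows.
3. Romidepsin is also possibly responsible. Section 7.7.2 calls for the most conservative approach, which plausibly points to stopping.

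Only the first branch is left open. Attribution to one drug is foreseen: Section 7.7.2 distinguishes it, and SAP 10.6.2 tabulates related events by suspected drug.

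**Size.** An affected patient must have a qualifying first event, restart at a lower dose, have a similar event again, have it attributed to Tenalisib alone, and recover within 2 weeks. The documents give no rate for this sequence. The planned maximum is 18 + 24 = 42 patients, unless dose levels are added.

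The Tenalisib-alone study in Section 1.1.2 (58 patients) lists 1 related neutropenia of Grade 3 or higher (1/58 = 1.7%) and no thrombocytopenia. Events that would fall in the last row of Table 8 number 4 rash + 2 hypophosphatemia + 1 INR + 1 pyrexia + 1 diplopia + 1 drug reaction = 10 (10/58 = 17.2%, if each is a different patient). None of these is reported as a recurrence at a reduced dose. The neutropenia count does not separate Grade 4 from Grade 3, and Table 7 maintains the dose at Grade 3. These rates therefore do not measure the problem and are not projected onto this trial.

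**The case against.** The strongest reply is that the cells give immediate management and Section 7.7 decides whether Tenalisib ever resumes. The first-occurrence text says to restart; the later-occurrence text does not. Section 7.7 is also worded as a recommendation with an exception, so holding a patient while approval is sought is consistent with it. Part of this stands: the two texts are not flatly opposite orders, and a hold has a use under both. But the cells go on to make discontinuation conditional on a further dose modification, whereas Section 7.7 makes it the default. Dose modification is undefined. If a hold counted as one, the condition would always be met, because the same cell orders the hold.

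A second reply is that other controls cover most cases. This stands and narrows the point. Romidepsin is myelosuppressive (Section 3.4.5.2) and toxicity is presumed treatment-related (Section 7.2), so many cytopenias will come under the most-conservative rule. Delays over 2 weeks already need Medical Monitor agreement. Regular Medical Monitor review of adverse events (Section 12.3) and SRC review every 3 months in expansion (Section 3.6.3) also provide oversight, but neither is approval before a restart.

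A reader might cite the Romidepsin rules as proof of intent. They support it only in part. The non-hematologic rule (7.7.3.2) stops Romidepsin when Grade 3 or 4 toxicity recurs after reduction; the hematologic rule (7.7.3.1) has no such text, and Section 7.7.3 leaves the number of reductions to the investigator.

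**Conclusion.** The inconsistency is real but limited: two cells in conflict and one in partial conflict, out of seven rows, with no order of precedence. It matters mainly for events attributed to Tenalisib alone that recover within 2 weeks. The number of patients is unknown and probably small. The conclusion rests on reading the cells' conditional stop as permitting continuation after recovery, and on the most-conservative rule settling events possibly related to both drugs.

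Three stronger readings should be resisted:

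- That dose finding is compromised. Sections 7.6 and 7.6.4 count patients with a qualifying toxicity in the first 28 days; what happens to Tenalisib after a later recurrence does not enter that count.
- That re-exposure is generally unsupervised. The 2-week agreement and the most-conservative rule say otherwise.
- That the SAP tables are wrongly specified. They are not; only the split between interruptions and permanent withdrawals can vary with the rule followed.

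Patients re-escalated under the intra-subject provision of Section 3.2.1.1 are no longer at the reduced dose and fall outside this point. The matter deserves correction at the next amendment because it concerns a safety rule and is cheap to settle.

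**What to change.** Reword the subsequent-occurrence text for Grade 4 neutropenia and Grade 4 thrombocytopenia in Table 7 to: *Recurrence at the reduced dose: hold and discontinue Tenalisib; resume after recovery to Grade 2 or less or baseline only in an exceptional case, after benefit-risk assessment and with Medical Monitor approval.*

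Use the same wording in the last row of Table 8 for recurrence of the same or a similar toxicity, and keep the present hold text there for a different Grade 3/4 toxicity.

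Add one sentence to Section 7.7: *The recurrence rule in this section, including Medical Monitor approval, prevails over all rows of Tables 7 and 8.* This also covers transaminitis, where the default already agrees but approval is not named.

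The cost is amendment wording for three cells and one sentence, plus a memo to sites; no procedure, visit or patient is added. The downside is that some patients will stop Tenalisib earlier or wait for approval, which Section 7.7 already requires.
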